Clinical Study Protocol

Drug Substance Durvalumab (MEDI4736)

Study Number **19-20015**

Edition Number: **4**

Date: **11 February 2022**

Investigational Drug **Durvalumab (MEDI4736)**

Substance(s) **Sirolimus (Rapamune)**

Study Number **19-20015**

Version Number **4**

Date

11 February 2022

A Phase 1b Neoadjuvant Trial of Sirolimus Followed by Durvalumab (MEDI4736) in Resectable Non-small Cell Lung Cancer

Supporter: AstraZeneca/MedImmune

Clinical Study Protocol

Drug Substance Sirolimus (Rapamune)

Study Number **19-20015**

Edition Number: 4

Date: 11 February 2022

PROTOCOL SYNOPSIS

Clinical Protocol ESR 19-20015

Study Title: A Phase 1b Neoadjuvant Trial of Sirolimus followed by Durvalumab (MEDI4736) in Resectable Non-small Cell Lung Cancer

Protocol Number: 19-20015

Clinical Phase: Ib

Study Duration: 4 years, which will include survival follow-up for up to 2 years after the last patient receives the last dose of neoadjuvant durvalumab

Investigational Product(s) and Reference Therapy:

Durvalumab (MEDI4736) solution for infusion after dilution will be supplied in glass vials containing 500 mg of liquid solution durvalumab at a concentration of 50 mg/mL infusion after dilution.

Sirolimus (Rapamune) will be supplied in 1 mg, white, triangular-shaped tablets marked “RAPAMUNE 1 mg” on one side; bottle containing 100 tablets.

Research Hypothesis

We hypothesize that administration of sirolimus, an mTOR inhibitor, followed by durvalumab, an engineered human IgG1 kappa monoclonal antibody targeting PD-1, will demonstrate a good safety profile and produce objective responses in clinical Stage I-IIIA NSCLC. We plan to assess established markers that correlate with response including PD-L1 expression in the tumors and tumor mutation burden by next generation sequencing. As these markers are not perfect and some patients with low PD-L1 and mutational burden may derive benefit, additional study of immune mechanisms is needed. Moreover, there is significant interest in developing combination therapy regimens that enhance the immune system response to cancer of patients that are PD-L1 and mutational burden low. Our focus on biomarkers of response will help identify patients who will benefit from this treatment strategy.

Objectives:

Co-Primary Objectives:

- To evaluate the safety and tolerability of sirolimus followed by durvalumab as neoadjuvant treatment

Clinical Study Protocol

Drug Substance Sirolimus (Rapamune)

Study Number **19-20015**

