Edition Number: **4**

Date: **11 February 2022**

- To evaluate the efficacy of sirolimus followed by durvalumab as neoadjuvant treatment for Stage I, II, and IIIA NSCLC

Secondary Objective(s):

- To evaluate the efficacy of sirolimus followed by durvalumab as neoadjuvant treatment for Stage I, II, and IIIA NSCLC
- To evaluate response to sirolimus followed by durvalumab in patients with PD-L1 positive vs. PD-L1-negative tumors
- To evaluate the association between blood mutation burden and response to sirolimus followed by durvalumab

Exploratory Objective(s):

- To evaluate the immune-mediated effects of sirolimus followed by durvalumab
- To investigate tumor and immune microenvironment changes in tissue samples

Study Design:

Up to 31 patients with NSCLC will be enrolled in this study at Emory University Winship Cancer Institute and associated clinical sites. Eligible patients will complete 3 weeks of daily oral sirolimus followed by 2 cycles of durvalumab treatment prior to proceeding to standard of care surgical resection. Durvalumab will be administered at a dose of 1500mg Q 3 weeks starting on C1D1 for up to 2 cycles that are 21 days in length. Pharmacodynamic analysis will be done using PD samples collected at baseline (tissue) and with blood samples on day 1, day 22 C1 prior to durvalumab, day 43 C2 durvalumab, and at the time of surgery (blood and tissue). Additional post surgery blood samples will be collected at 1-, 3-, and 6-months post-surgery. See Appendix D for schedule of Biomarker collection. Patients will proceed to surgery within a 2–3-week period post 2nd dose of durvalumab but not earlier than two weeks after the administration of durvalumab i.e. not earlier than C2D14. Additionally, as an optional study, patients will self-administer heavy water (D2O) 50ml orally three times a day from day 22 C1 through day 27 followed by 50ml orally twice a day through the day prior to surgery in order to label dividing cells for research tracking purposes.

Number of Centers: Emory University Winship Cancer Institute and affiliated hospitals

Number of Patients: 31

Study Population: Resectable Stage 1-3A NSCLC

Inclusion Criteria:

- Pathologically documented NSCLC who are candidates for surgical resection
- Capable of signing informed consent

- Age \geq 18 years at time of study entry.
- Eastern Cooperative Oncology Group (ECOG) performance status of 0 or 1
- Life expectancy of \geq 26 weeks
- Body weight >30 kg

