- Judgment by the investigator that the patient is unsuitable to participate in the study and the patient is unlikely to comply with study procedures, restrictions and requirements.

Investigational Product(s), Dose and Mode of Administration:

Patients will receive 1500 mg durvalumab via IV infusion Q3W for up to a maximum of 2 cycles prior to curative resection surgery. Weight-based dosing (20 mg/kg) should be utilized for patients whose body weight falls to <30 kg while on study.

Patient will self-administer sirolimus 6 mg orally once on day 1, followed by once daily dosing of 2mg, continuously through day 21, which is one day prior to C1 of durvalumab. The dose should be taken each morning, with or without food.

Study Assessments and Criteria for Evaluation:

Safety Assessments:

- Incidence of adverse events, with severity per NCI CTCAE v5.0
- Length of hospital stay after surgery

Efficacy Assessments:

- Complete pathologic response, scored by a pathologist, based on surgical resection as defined by prior studies
- Investigator-assessed response rate per RECIST v1.1
- DFS and OS
- Pathological response in PD-L1-positive and PD-L1-negative groups
- Overall response rate in PD-L1-positive and PD-L1-negative groups based on mutational burden

Statistical Methods and Data Analysis:

Safety Analyses:

All enrolled patients will be evaluable for safety analyses from the time of their first treatment with sirolimus. After study complete, DLTs will be summarized and tabulated by type and grade. DLT rate

by dose level will be calculated as proportion (Patients with DLT/Total patients) along with 95% confidence intervals using the Clopper-Pearson method. Chi-square test or Fisher's exact test will be used to compare the probability of DLT between the different other factors, such as PD-L1 status, dose levels, etc. respectively.

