A comparison of both the *complete pathologic response* and investigator assessed response rates per RECIST v1.1 rates between the PD-L1 positive and PD-L1 negative groups will be performed by calculating the lower bound of a one-sided 80% CI for the difference, complete pathologic response for PDL-1 positive patients – complete pathologic response for PDL-1 negative patients. Chi-square test or Fisher's exact test will be used to compare the efficacy in term of response rate between the different groups stratified by other factors, respectively. Logistics regression model will be further employed to test the adjusted effect of each other factor on the response rate after adjusting for other clinical factors and demographic factors, respectively. Correlation of response will be performed for tumor mutation burden using spearman correlation coefficient and tested with Wald's test.

Sample Size Determination:

Pathologic complete response is rare following neoadjuvant chemotherapy but was reported in 0-8% of cases³⁹. The current study is designed to test improved rate of pathologic complete response from 10% to 25% with sequential treatment with sirolimus and durvalumab. Using a MinMax 2-stage design, a total of 31 patients will be enrolled in 2 stages. At the end of stage I, at least 2 of 16 patients must achieve complete pathologic complete response in order for the study to enroll 15 additional patients. The regimen of sirolimus followed by durvalumab will be considered to have sufficient efficacy to warrant further testing in this patient population if 6 or more of the 31 patients achieve a pathologic CR at the end of stage II. The study has 80% power at a 1-sided alpha of 0.1 to show a compelling 25% pCR compared to a less compelling rate of 10%. Because this is a signal finding study, an alpha of 0.1 is considered reasonable since any promising signal will be confirmed in a larger follow-up study.

Clinical Study Protocol

Drug Substance Sirolimus (Rapamune)

Study Number **19-20015**

Edition Number: **4**

Date: **11 February 2022**

SCHEDULE OF STUDY ASSESSMENTS

	Screening	Sirolimus	Durvalumab C1	Durvalumab C2	Pre- surgery	Surgery	Study DC	Follow- up	For details see Section				
Week	-4 to 0	0	3	6	8-9		Post Surgery 30 +/- 7 days	Every 3 months for 2 years					
Day	-28 to 0	1-21	22 +/- 3 days^a	43 +/- 3 days^a	57-64 +/- 10 days								
Informed Consent													

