2.2 Secondary objective(s)

- To evaluate the efficacy of sirolimus in combination with durvalumab as neoadjuvant treatment for Stage I, II, and IIIA NSCLC by Investigator-assessed response rate per RECIST v1.1, disease free survival and overall survival
- To evaluate response to sirolimus in combination with durvalumab in patients with PD-L1-positive vs. PD-L1-negative tumors by complete pathologic response rate
- To evaluate the association between blood mutation burden and response to sirolimus and durvalumab by overall response rate in PD-L1-positive and PD-L1-negative groups based on mutational burden.
- To evaluate impact of neoadjuvant durvalumab and sirolimus on post-surgical recovery by length of hospital stay after surgery

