11.2.2 Efficacy analyses

Primary Efficacy Endpoint

The effectiveness of sirolimus followed by durvalumab will be assessed by complete pathologic response rate in the efficacy population. If the null hypothesis is rejected then this is evidence that the response rate exceeds 10% when sirolimus followed by durvalumab is given before resection. The one-sided 95% confidence interval (CI) for complete pathologic response will be reported. Exact binomial test will be used to compare the estimated complete pathologic response rate to the historical reference.

Secondary Efficacy Endpoints

The complete pathologic response rates for PDL-1 negative and PDL-1 positive patients in the *efficacy population* will be presented separately.

A comparison of both the *complete pathologic response* and investigator assessed response rates per RECIST v1.1 rates between the PD-L1 positive and PD-L1 negative groups will be performed by calculating the lower bound of a one-sided 80% CI for the difference, complete pathologic response for PDL-1 positive patients – complete pathologic response for PDL-1 negative patients. Chi-square test or Fisher's exact test will be used to compare the efficacy in term of response rate between the different groups stratified by other factors, respectively. Logistics regression model will be further employed to test the adjusted effect of each other factor on the response rate after adjusting for other clinical factors and demographic factors, respectively. Correlation of response will be performed for tumor mutation burden using spearman correlation coefficient and tested with Wald's test.

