11.3 Determination of sample size

Pathologic complete response is rare following neoadjuvant chemotherapy but was reported in 0-8% of cases³⁹. The current study is designed to test improved rate of pathologic complete response from 10% to 25% treatment with sirolimus followed by durvalumab. Using a MinMax 2-stage design, a total of 31 patients will be enrolled in 2 stages. At the end of stage I, at least 2 of 16 patients must achieve complete pathologic complete response in order for the study to enroll 15 additional patients. The regimen of sirolimus followed by durvalumab will be considered to have sufficient efficacy to warrant further testing in this patient population if 6 or more of the 31 patients achieve a pathologic CR at the end of stage II. The study has 80% power at a 1-sided alpha of 0.1 to show a compelling 25% pCR compared to a less compelling rate of 10%. Because this is a signal finding study, an alpha of 0.1 is considered reasonable since any promising signal will be confirmed in a larger follow-up study.

Planned total number of patients is 31 over 2 years, with an estimated accrual rate of approximately 1-2 patients/month. Racial, ethnic, and gender accrual estimates below are based on 2010 Atlanta Census demographic information.

Accrual Targets			
Ethnic Category	Sex/Gender		
	Females	Males	Total
Hispanic or Latino	1	+ 1	= 2
Not Hispanic or Latino	14	+ 14	= 28
Ethnic Category: Total of all subjects	15 (A1)	+ 15 (B1)	= 30 (C1)
Racial Category			
American Indian or Alaskan Native	0	+ 0	= 0
Asian	1	+ 1	= 2
Black or African American	6	+ 6	= 12

Clinical Study Protocol

Investigational Drug Substance: MEDI4736 Sirolimus (Rapamune)

Study Number **19-20015**

Edition Number: 4

Date: **11 February 2022**

Native Hawaiian or other Pacific Islander	1	+	1	=	2
White	7	+	7	=	14
Racial Category: Total of all subjects	15	(A2)	15	(B2)	30 (C2)
(A1 = A2)		(B1 = B2)		(C1 = C2)	

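### The adjusted response model leaves open which response is modelled and how many covariates enter, and ordinary fitting can break down at about 4 to 8 pCRs; the mutation-burden objective and its analysis do not match

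*Combined protocol and SAP*

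**What the plan says.** Under Secondary Efficacy Endpoints, Section 11.2.2 and the synopsis first compare pCR and investigator-assessed RECIST v1.1 response between PD-L1 groups, and plan unadjusted chi-square or Fisher tests. They then add: "Logistics regression model will be further employed to test the adjusted effect of each other factor on the response rate". The adjustment set is described only in general terms, as clinical and demographic variables. No factor or covariate is named, and no test or fitting method is given for the model. Wald's test appears in the following sentence, but it belongs to the Spearman correlation.

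Section 11.3 sets a two-stage design in 31 patients, testing pCR of 10% against 25%: "at least 2 of 16 patients must achieve complete pathologic complete response in order for the study to enroll 15 additional patients".

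On mutation burden, the secondary objective in Section 2.2 is "To evaluate the association between blood mutation burden and response to sirolimus and durvalumab by overall response rate", within PD-L1-positive and PD-L1-negative groups. The synopsis objective is "To evaluate the association between blood mutation burden and response to sirolimus followed by durvalumab", and its efficacy assessments list "Overall response rate in PD-L1-positive and PD-L1-negative groups based on mutational burden". The analysis in Section 11.2.2 is "Correlation of response will be performed for tumor mutation burden using spearman correlation coefficient".

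**The concern.** An adjusted logistic model needs enough events for its odds ratios to be estimable and its test to hold its level. With a handful of pCRs, one level of a factor can easily contain no responders or only responders. Ordinary maximum likelihood then gives no finite odds ratio, and the likelihood-ratio and Wald tests can disagree sharply. Because the outcome, covariates and test are open, all three could be settled after the data are seen. Identifying the patients who benefit is a stated aim (synopsis and Section 1.4), so the adjusted results are likely to be read.

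The mutation-burden objective is a separate matter. If objective and analysis name different measurements and endpoints, the objective has no analysis that answers it as written.

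**Working it through.** **Inputs.** From Section 11.3: pCR 10% versus 25%, 16 + 15 patients, continue at 2 or more of 16, success at 6 or more of 31. The efficacy population (Section 11.1.2) is taken to be all 31, which is an assumption. The documents give no planning rate for RECIST response, so the counts below concern pCR only.

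**Plan's own figures.** P(success) is the sum over x from 2 to 16 of P(X1 = x) × P(X2 ≥ 6 − x), with X1 binomial in 16 and X2 binomial in 15. This gives 0.0788 at 10% and 0.805 at 25%, within the stated alpha of 0.1 and 80% power. A minimax search returns the stated design.

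**Expected pCRs once stage 2 is reached.** The mean is [16p − P(X1 = 1)] / [1 − P(X1 = 0) − P(X1 = 1)] + 15p.

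- At 10%: (1.6 − 0.329) / (1 − 0.185 − 0.329) + 1.5 = 2.62 + 1.5 = 4.12.
- At 25%: (4 − 0.053) / (1 − 0.010 − 0.053) + 3.75 = 4.21 + 3.75 = 7.96.

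Without conditioning on stage 2, the means are 3.1 and 7.75. Five model terms would leave 4.12/5 = 0.8 to 7.96/5 = 1.6 events per term.

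**One balanced binary factor with no effect.** Given k responders, the odds ratio is non-finite essentially when all responders fall in one level, with probability 2 × 0.5^k. The corresponding event among the non-responders is negligible. Weight this by the chance of k, given stage 2:

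| k | P(k) at 10% | P(k) at 25% | 2 × 0.5^k |
|---|---|---|---|
| 2 | 0.116 | 0.002 | 0.500 |
| 3 | 0.255 | 0.013 | 0.250 |
| 4 | 0.273 | 0.040 | 0.125 |
| 5 | 0.193 | 0.085 | 0.063 |
| 6 | 0.101 | 0.134 | 0.031 |
| 7 | 0.042 | 0.166 | 0.016 |
| 8 | 0.014 | 0.170 | 0.008 |

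The products sum to about 0.17 at 10% and, with the small terms beyond k = 8, to about 0.023 at 25%. The same sum at 20% gives 4.8%.

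**More terms, and a real effect.** These figures come from simulation of trials that reach stage 2, with 1 to 5 terms. The first two terms are binary at 50%, the rest are standard normal, and only the first has an effect. All of this is assumed, because the plan fixes no model. The share of trials in which some coefficient has no finite ordinary estimate is:

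| True pCR | No effect | Odds ratio 3 |
|---|---|---|
| 25% | about 2-5% | about 8-10% |
| 10% | about 17-35% | about 31-43% |

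**Null rejection at nominal two-sided 5%.**

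| Test | Rejection rate |
|---|---|
| Ordinary Wald (non-finite fits counted as non-rejections) | about 0.1-3% |
| Ordinary likelihood ratio, 1-2 terms | about 6-10% (exactly 6.3% for one term at 25% pCR) |
| Ordinary likelihood ratio, more terms | up to about 16% at 10% pCR |
| Firth profile likelihood | about 2-5% |

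**Mutation burden, side by side.**

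| | Objective (synopsis, 2.2) | Analysis (11.2.2) |
|---|---|---|
| Measurement | blood mutation burden | tumor mutation burden |
| Endpoint | overall response rate (2.2) | response, unspecified |
| PD-L1 grouping | within PD-L1 groups (2.2) | none |

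Other sections do not resolve this. The hypothesis speaks of "PD-L1 expression in the tumors and tumor mutation burden by next generation sequencing". Section 8.2.1 plans a tumor gene panel without promising a burden score. Section 8.2.2, headed as blood-based studies, lists tumor mutation burden among analyses that may be done. Section 11.2.3 covers sequencing of both tumor tissue and normal blood or tissue, with mutation burden among the outputs.

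**The case against.** The strongest case against has five parts.

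- **The outcome is not wholly unnamed.** The sentence says response rate, in a paragraph that uses exactly two. This stands: the defect is ambiguity between two named endpoints, not a missing one.
- **The large figures come from an unfavourable corner.** The 31-43% needs a true pCR of 10%, an odds ratio of 3, and survival of a stage 1 rule that stops 51.5% of such trials. At the design alternative of 25%, ordinary fitting gives finite estimates in about 90% or more of trials. This also stands. A reader might infer that the planned model will fail; the calculations support only that it can.
- **Wald is conservative here and would not create false signals.** That is correct, but the plan names no test for this model, and the likelihood-ratio test errs in the other direction.
- **The remedy changes little.** Firth power for an odds ratio of 3 is only 21-24% at 25% pCR and 8-12% at 10%. Low power stands under any method. The gain is finite estimates and a controlled error rate.
- **This is a signal-finding trial with confirmation planned.** That argues for low severity, and for an exploratory label. The label cannot be assumed, since the model sits under secondary endpoints and not in Section 11.2.3.

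A reader might also infer that blood is simply the wrong word in the objective, because the hypothesis and analysis say tumor. The documents do not support that ruling: a tumor mutation burden measured in blood would be compatible with Section 8.2.2, and Section 11.2.3 does not settle it.

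**Conclusion.** The point holds as a cheap improvement of low severity. The adjusted model is ambiguous between two responses and unlimited in covariates. If it is fitted to pCR with about 4 to 8 events, ordinary maximum likelihood can give a non-finite odds ratio, uncommonly at 25% pCR and often at 10%, and the error rate depends on an unstated choice of test.

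The sizes rest on assumed balanced factors, independent covariates, illustrative model sizes and all 31 patients being analysed. Exclusions for no resection or EGFR mutation would generally lower the event count. Nothing here can be sized for RECIST response.

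The mutation-burden mismatch rests on the text alone: objective and analysis differ in measurement, endpoint and PD-L1 grouping.

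It would be wrong to infer that the trial's main conclusion is at risk. The primary pCR test, the stage rules, the unadjusted chi-square or Fisher tests and the one-sided 80% interval for the PD-L1 difference are not affected.

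**What to change.** In Section 11.2.2 and the synopsis, state that adjusted response models:

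- name the response modelled, pCR or RECIST v1.1;
- use one or two covariates named in advance;
- are fitted by Firth-penalised (or exact) logistic regression with profile-likelihood (or exact) intervals;
- are exploratory.

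Reconcile the mutation-burden objective (synopsis and Section 2.2) with the analysis in Section 11.2.2, so that both give the same measurement, the same response endpoint and the same decision on PD-L1 grouping. Align Sections 8.2.1, 8.2.2 and 11.2.3 with that choice.

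The cost is a few sentences and a different software procedure, with no change to sample size or conduct. At very low pCR the Firth estimate is pulled toward no effect, by about 8-11% on the log odds ratio scale at 10% pCR with a true odds ratio of 3, and power stays low.

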11.2.3 Exploratory analyses

Exploratory biomarker analyses will be performed to explore the relationship between the clinical outcomes and the immunological, pathological and genomic characteristics of the cancers. Biomarker analyses may include, but may not be limited to, the analyses described below.

- A detailed pathological evaluation will be performed on the surgically resected samples.
- Immunologic analyses by IHC, IF, and flow cytometry
- Genomic analysis may include DNA sequencing (NGS or WES) and RNA sequencing from tumor tissue and normal blood/tissue, to identify mutations, mutation burden, gene expression profiles and associations with treatment response.

11.2.4 Interim analyses

There will be a safety assessment following the completion of surgery for the first six patients on the protocol. Both the DLT assessment and Enrollment will continue during this time. There will be an analysis of the pCR rate of the 16 patients included in the first stage of the design.

